content of cigarettes was withheld. These study designs, while able to evaluate the influence of nicotine reduction per se on relevant outcomes, do not adequately simulate a real world marketplace in three major ways. First, with a national nicotine reduction policy, no regular nicotine cigarettes would be available and alternative nicotine-containing products would be widely available. Therefore, the impact of such a policy on the use of other tobacco or nicotine products needs to be considered to fully understand public health effects. Second, providing cigarettes for free is likely to underestimate the degree to which RNC cigarettes might impact smoking behavior. If smokers were required to pay \$6 to \$10 for a pack of cigarettes that they find relatively non-rewarding, they are likely to smoke fewer cigarettes than they would if these products are provided at no cost.¹⁴ The importance of price on consumption is widely known and is the basis of increasing taxes on cigarettes to drive the prevalence of smoking down.¹⁵ Third, with the implementation of a reduced nicotine policy, the FDA would by necessity provide information to consumers on the reduced nicotine content of cigarettes. The knowledge of nicotine content in cigarettes might influence expectancies or beliefs about the cigarettes, which then might affect smoking uptake or behavior. With respect to simulating the consumer, another limitation of prior studies is the recruitment of a relatively narrow selection of smokers in most studies. That is, smokers were recruited only if they were not motivated to quit smoking and used minimal amounts of other tobacco products. In a recent large clinical trial, about 15% were excluded for using other tobacco products (e.g., greater than 9 times per month) and 7% were excluded because they were motivated to quit in the next 30 days, thus omitting almost a quarter of the sample. All these limitations demonstrate the need to conduct a study that includes a more broadly selected sample of smokers and that better approximates the marketplace that is likely to occur if the policy to reduce nicotine in cigarettes is implemented.

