5.2.4. Phase 2: Marketplace Adaptation Visit (00) Procedures

A. Physiological Measures at MP 00:

- 1) BrAC (discontinued at telehealth visits).
- 2) Expired breath CO level.
- 3) Vitals signs (blood pressure, heart rate).
- 4) Weight.
- 5) First morning void urine.
- 6) Spot urine for pregnancy tests [hCG detection] will be performed for female participants of childbearing potential (not surgically sterilized or 2 years post-menopausal) at Week 00. (Pregnancy tests are performed on first morning void after conversion to telehealth visits.)

B. Questionnaires and Assessments at MP 00:

B.1 Web-based data collection program completed by the subject:

- 1) Minnesota Nicotine Withdrawal Scale (MNWS).
- 2) Questionnaire of Smoking Urges-Brief -Usual Cigarette (QSU).
- 3) Cigarette & Product Evaluation Scale – (Baseline Usual Brand CES/PES).
- 4) Respiratory and Global Health Questionnaire.
- 5) CES-D:
Beck Depression Inventory 2nd Edition (BD-II) will be administered on paper if the CES-D score is 16 or greater or if monitored for psychiatric illness.
- 6) Cigarette Dependence Measures (Usual brand)
- 7) Environmental Tobacco Smoke Exposure Questionnaire
- 8) Dietary Intake.
- 9) NIAAA Alcohol Use Questionnaire (1 month).
- 10) Perceived Health Risk of no tobacco use, usual brand cigarettes, very low nicotine cigarettes, smokeless tobacco, medicinal nicotine and ENDS.
- 11) Contemplation Ladder.
- 12) Cigarette (Usual Brand and All Products) Purchase Task.

B.2 Administered as an interview by the study Research Assistant (entered into REDCap):

- 1) Health Changes Questionnaire.
- 2) Adverse Events.
- 3) Concomitant Medications.
- 4) Review of Daily Call and follow-up of missing and unusual reports.
- 5) Timeline Followback Questionnaire.
- 6) Recreational Drug Use Questionnaire (1 month version).
- 7) Product Accountability: Complete Product Dispensing Log.
- 8) Study Product and Procedures Compliance Review.
- 9) End of Visit Questionnaire.

Randomization and Marketplace with study cigarettes

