- 15) *Cigarette/Product Purchase Task* assesses demand curves of products that are chosen.^{48,49} This task will be used to generate demand curves by asking the subject to report the number of units of a tobacco product that they would consume in a day if the units cost various amounts of money.
- 16) *Product Expectancy Questionnaire* to assess attitudes and beliefs about the products provided.
- 17) *Expected Utility (Alternative Nicotine Products) Questionnaire* assesses the situations or expected uses of the study products.
- 18) *Contemplation Ladder⁵⁰* assesses intention to quit smoking including next 30 days and 6 months and overall readiness to quit.⁵¹
- 19) *Social and Environmental Influences on Tobacco Use* assesses tobacco/nicotine situational use and subject's opinion on potential tobacco control policies.
- 20) *End of Study Questionnaire*, administered at follow-up to assess subject responses to study products and study experience.

6. Collection and Sharing of Biomarker Specimens and Data

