Demographics	EDC	X												
Brief Medical History	Paper and REDCap	X												
PHQ PrimeMD (Beck if applicable)	Paper and REDCap	X												
CES-D	EDC	X					X		X		X		X	X
Beck Depression Inventory/GAD (if + PHQ or Elevated CES-D)	Paper and REDCap	X	X	X	X	X	X	X	X	X	X	X	X	X
(MINI) Suicide Subscale	On Paper only	X												
Drug Abuse Screening Test (DAST)	EDC	X												
Alcohol Use Questionnaire 12 mo	EDC	X												
Drug Use Questionnaire 12 mo	Paper and REDCap	X												
Michigan Alcohol Screening (SMAST)	EDC	X												
Assessment Name	Platform	SCRN 94	BL 93	BL 92	MP 91	MP 00	Week 1-3 ³	Week 4	Week 6	Week 8	Week 10	Week 12	F-Up 16	Early Term

Assessment Name	Platform	SCRN 94	BL 93	BL 92	MP 91	MP 00	Week 1-3 ³	Week 4	Week 6	Week 8	Week 10	Week 12	F-Up 16	Early Term
TOBACCO USE MEASURES														
Daily Call (IVR-tobacco diary)	IVR		X	X	X	X	X	X	X	X	X	X		X
Timeline Follow-back	Paper and REDCap		X	X	X	X	X	X	X	X	X	X	X	X
IVR Review	Paper and REDCap		X	X	X	X	X	X	X	X	X	X	X	X
ADVERSE CONSEQUENCES														
MNWS	EDCs		X	X	X	X	X	X	X	X	X	X		
QSU- Usual cigarettes	EDC		X	X	X	X								
QSU - Study cigarettes	EDC						X	X	X	X	X	X		
Alcohol Use Questionnaire 1 mo.	EDC		X			X		X		X		X		X
Drug Use Questionnaire - 1 month	Paper and REDCap		X			X		X		X		X		X
Respiratory & Global Health Quest.	EDC		X	X	X	X	X	X	X	X	X	X	X	X
DEPENDENCE MEASURES														
Cigarette Dependence Scale (FTND, PATH items, WISDM subscale)	EDC		X			X		X		X		X	X	X
Vaping/Product Dependence Scale	EDC												X	X
Severson SLT Dependence Scale													X	
Contemplation Ladder	EDC			X		X								
ACCEPTABILITY MEASURES														
Cigarette Eval. Scale Usual brand	EDC		X	X	X	X							X	X
Cigarette Eval. Scale Study cigs	EDC						X	X	X	X	X	X		X
Product Eval. Scale (all selected)	EDC				X	X	X	X	X	X	X	X		X
Perceived Health Risk Rating	EDC			X		X							X	
Cigarette Purchase Task - Usual Cigs	EDC			X		X							X	
Cigarette Purchase Task - Study Cigs	EDC												X	
Product Purchase Task - All products	EDC			X		X							X	
Assessment Name	Platform	SCRN 94	BL 93	BL 92	MP 91	MP 00	Week 1-3 ³	Week 4	Week 6	Week 8	Week 10	Week 12	F-Up 16	Early Term

Assessment Name	Platform	SCRN 94	BL 93	BL 92	MP 91	MP 00	Week 1-3 ³	Week 4	Week 6	Week 8	Week 10	Week 12	Follow -Up 16	Early Term
Biomarker Modifiers														
Dietary Intake	EDC		X			X		X		X		X		X
Environmental Tobacco Exposure	EDC		X			X		X		X		X		X
OTHER														

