5.1. Primary Endpoints

- Cigarettes per day (CPD): the mean cigarettes (study and non-study cigarettes) smoked per day based on 7 days' Daily Interactive Voice Response (IVR)-Revised (corrected with participant for errors) data before the week 12 visit.
- Smoke-free days during Phase 3: the number of days not smoking any combustible products based on IVR-Revised.

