6.2. Describing the Study Population

Descriptive statistics will be performed for data collected at different visits. Daily Interactive Voice Response (IVR) data will be summarized by phase and by visit (according to the actual visit dates or scheduled visit dates if a visit is missed). Baseline data will be compared between the two studied conditions with t test or Wilcoxon rank sum test

for continuous variables and chi-square test or Fisher's exact test for categorical variables, which include sex, age, race, education, menthol status, dependence (FTND), CPD, nicotine metabolite ratio (NMR), and TNE. Baseline CPD and TNE are based on Phase 2.

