6.3.1. Primary Analysis

We expect the two groups to, on average, be balanced for important baseline characteristics due to randomization, so the primary analyses will be regressions for the difference in CPD and the number of smoke-free days between two conditions, adjusting for only the baseline value (the mean CPD and the percent of smoke-free days during Phase 2, respectively). Specifically, for the CPD outcome at week 12, we will use linear regression; for the number of smoke-free days, we will use Poisson regression or negative binomial regression when there is over-dispersion in the count data.

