6.5. Exploratory Endpoint Analysis

- For the number of days of non-combusted tobacco/nicotine products use, we will use Poisson or negative binomial regression, adjusting for baseline value, study site, whether the visit is pre-COVID or not, and any baseline characteristics which are different at $p < 0.20$.
- We will descriptively examine the characteristics of the various products that are chosen (type, nicotine strength, flavor).
- For other biomarkers, similar analyses to Secondary Endpoint will be performed.
- Product satisfaction (Product Evaluation Scale, Cigarette Evaluation Scale) at the first time a participant tried a product will be summarized using mean and standard deviation and compared between two treatment arms using linear regression.
- Repeated measures of perceived health risk will be analyzed using the mixed effects model as described in Section 6.3.2.
- Discomfort as assessed by MNWS-R, QSU, CESD will be compared between the VLNC vs. NNC cigarette conditions. The methods for comparing discomfort measures between VLNC and NNC cigarettes will be the same as for those described for the primary endpoints in Section 6.3.
- Repeated measures of dependence of study cigarettes will be analyzed using mixed effects model described in Section 6.3.2.
- We will examine the cross-sectional associations of non-combusted products use with cigarettes smoked and biomarkers at different visits using marginal generalized estimating equations (GEE) model (Diggle et al, 2002, Chapter 12) with the non-combusted product use as the independent variable.
- We will explore baseline predictors of responses. We will use multivariable regressions to determine predictors of product use patterns, e.g., non-combusted product use, combusted product use, and smoke-free days. Predictor variables (depending on the responses measured) will include baseline CPD, total nicotine equivalents, FTND, age, sex, racial ethnic group, SES, perceived risk of products, product expectancy, product utility, social and environmental influences, contemplation ladder, menthol cigarette use, and nicotine metabolite ratio (NMR, reflecting rate of nicotine metabolism). Similar regression models as described in Sections 6.3 and 6.4 will be used.

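### Quit intention is measured before randomisation but is missing from the SAP 6.2 list, so the adjusted models for smoke-free days and 7-day abstinence cannot include it

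*Combined protocol and SAP*

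**What the plan says.** SAP 5.1 defines the second primary endpoint as "Smoke-free days during Phase 3: the number of days not smoking any combustible products based on IVR-Revised". SAP 5.2 adds 7-day abstinence with CO verification as a secondary endpoint.

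Protocol 5.7.5 says the Contemplation Ladder "assesses intention to quit smoking including next 30 days and 6 months and overall readiness to quit". Protocol 5.2.4 includes it among the Visit 00 questionnaires ("11) Contemplation Ladder"), and the procedure table in section 27 also marks it there. Randomisation takes place at the end of that visit.

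The SAP then treats the ladder in two ways:

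- **SAP 6.5** (exploratory) plans regressions of product-use patterns, with smoke-free days as one example. Its predictors include "contemplation ladder, menthol cigarette use, and nicotine metabolite ratio".
- **SAP 6.2** names the baseline variables compared between arms, "which include sex, age, race, education, menthol status, dependence (FTND), CPD, nicotine metabolite ratio (NMR), and TNE". The ladder is not there. Protocol 16.6.2 gives the same nine variables.

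The primary model in SAP 6.3.1 is fitted "adjusting for only the baseline value". The adjusted analysis in 6.3.2 adds site, COVID period and those characteristics on the 6.2 list that differ between arms at p<0.20, and it gives efficiency as the reason. SAP 6.4 applies similar adjusted methods to the secondary endpoints, with logistic regression for abstinence.

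**The concern.** Both outcomes are about not smoking, and the trial deliberately broadens the range of quit intention. Protocol 2.3 criticises earlier studies in which "smokers were recruited only if they were not motivated to quit smoking and used minimal amounts of other tobacco products". No exclusion criterion here removes motivated smokers, and randomisation is stratified by site only.

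Quit intention is therefore a natural baseline covariate for smoke-free days and abstinence. It is free of treatment influence and is already collected. Because the adjusted models draw on a list that omits it, a chance difference between arms would not be tested and could not trigger adjustment. Any outcome variation it explains would stay in the residual of an analysis whose stated purpose is efficiency.

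**Working it through.** **Which models can contain the ladder**

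| Analysis | Covariates | Ladder possible? |
|---|---|---|
| SAP 6.2 comparison of arms | nine named variables | not named |
| SAP 6.3.1 primary | outcome's own Phase 2 value | no |
| SAP 6.3.2 adjusted | baseline value, site, COVID period, 6.2 variables at p<0.20 | no |
| SAP 6.4 abstinence | as 6.3.2, logistic | no |
| SAP 6.5 predictors | list includes the ladder | yes, exploratory |

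**The plan's own power for smoke-free days**

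Inputs: NNC rate r0 = 0.0504 (SAP Table 1); difference d = 11/84 = 0.1310; r1 = 0.1814; two-sided alpha 0.025, so z = 2.241; 20% attrition, so n = 0.4N per arm.

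Power = Φ(d/√((r0+r1)/n) − z)

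- N=450, n=180: 0.1310/0.03588 = 3.650, power .920 (stated .92)
- N=400, n=160: 0.1310/0.03806 = 3.441, power .885 (stated .88)

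**Precision from adjusting**

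The documents give no ladder-outcome correlation, so a range is assumed. A correlation ρ of 0.25 to 0.4 with the person-level propensity gives ρ² = 0.06 to 0.16. The usable gain is smaller, because day-to-day variation remains and Phase 2 smoke-free days already carry part of the information.

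This was simulated with 180 per arm, 84 days, arm means of 4.2 days (0.0504 × 84) and 15.2 days, a logit-normal propensity, 14 Phase 2 days in the model, Poisson log link with robust variance, and 300 runs per setting. The table shows the cut in mean model-estimated variance of the log rate ratio when the ladder is added.

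| Propensity SD | Phase 2–Phase 3 propensity correlation | ρ = 0.25 | ρ = 0.4 |
|---|---|---|---|
| 2 | 1.0 | 2.6% | 5.3% |
| 2 | 0.5 | 3.1% | 8.4% |
| 3 | 1.0 | 1.1% | 2.9% |
| 3 | 0.5 | 2.3% | 7.2% |

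A separate simulation over the same range of ρ, also with Phase 2 smoke-free days in the model, gave about 3% to 10%. The smallest gains arise when Phase 2 behaviour reflects exactly the same propensity as Phase 3. With SD 3 in that case, the run-to-run variances did not separate the gain from zero.

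For scale only, put a variance cut c into the plan's formula by dividing the standard error by 1/√(1−c):

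- N=450: .920 becomes .928 (c = 0.03) or .946 (c = 0.10)
- N=400: .885 becomes .895 or .917

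**Chance imbalance**

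A continuous covariate reaches p = 0.20 at a standardised difference of 1.282 × √(2/n), which is 0.135 at n=180 and 0.143 at n=160. With an assumed within-arm correlation of 0.1 to 0.3 with the outcome, the unadjusted estimate moves by 1.282 × 0.1 = 0.13 to 1.282 × 0.3 = 0.38 of its standard error.

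**Listing alone is not enough**

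Under randomisation the p<0.20 screen admits any one variable in about 20% of trials. A ladder that is only listed would be left out of the adjusted model about four times in five.

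**The case against.** The strongest reply is that a sparse, pre-specified primary model is a legitimate choice and that SAP 6.3.1 gives its reason. That stands. A reader might infer that omitting the ladder biases the primary test. It does not: randomisation protects the comparison, and chance imbalance is already reflected in the standard error.

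Three other strong readings also go beyond the documents:

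- **That the SAP establishes the ladder as a predictor.** SAP 6.5 treats it as one exploratory candidate among many. SES, perceived risk, product expectancy and others are on the same list and also absent from 6.2. Singling out the ladder is a judgement, based on quitting-type endpoints and the broadened recruitment.
- **That quit intention enters no model and is never shown.** The 6.5 regressions include it and use models similar to 6.3 and 6.4; whether treatment group stays in them is not stated. SAP 6.2 also promises descriptive statistics for data from the visits, without committing to a ladder table by arm.
- **That imbalance could move the result by 1 to 2 days.** Protocol 2.3 mentions 7% excluded from an earlier trial as motivated to quit within 30 days. At 200 per arm the standard error of a difference in that share is √(2 × 0.07 × 0.93/200) = 0.0255, so about 5 points is within chance. Reaching 1 to 2 days requires 20 to 40 extra smoke-free days per such smoker, which the documents do not supply. It would also be only about 0.5 to 1.3 standard errors, taking a simulated standard error of 1.6 to 2.0 days, against an 11-day target.

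Timing matters too. The synopsis closes enrolment on 9/30/2022 and the SAP was last modified on 11/21/2022. Changing a primary model that late in an open-label trial is hard to justify for this gain.

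**Conclusion.** The gap is real but modest. The ladder is a valid pre-randomisation covariate that the SAP considers worth exploring for smoke-free days, yet the wording of 6.2, 6.3.2 and 6.4 keeps it out of the adjusted treatment-effect models. Reading the 6.2 list as merely illustrative does not help, because 6.3.2 confines its candidates to what that section lists.

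The cost is a variance for the log rate ratio that is roughly 3% to 10% larger than it need be, with gains nearer 1% or not detectable in the least favourable settings, together with an untested chance imbalance. These figures rest on the assumed correlation of 0.25 to 0.4 and on the simulated person-level variation; neither comes from the documents. The 6.3.1 primary test and its stated power are unaffected.

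**What to change.** 1. Add the Visit 00 Contemplation Ladder score to the baseline list in SAP 6.2 and protocol 16.6.2, compared by arm.
2. Before outcomes are analysed by arm, pre-specify it as a fixed covariate, whatever the p<0.20 screen shows, in the adjusted smoke-free-days model (SAP 6.3.2; protocol 16.6.3, Secondary Analysis) and in the 7-day abstinence logistic model (SAP 6.4; protocol 16.6.4).
3. Leave the SAP 6.3.1 primary model as it is.

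Name the Visit 00 value explicitly. The text places the earlier ladder assessment at Screening and the procedure table places it at Visit 92, but both agree on Visit 00.

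No new data are needed. The cost is a dated SAP and protocol revision with a short rationale and a statement that outcomes had not been examined by arm, plus one more covariate. The abstinence odds ratio becomes conditional on quit intention, and the report should say so.

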5.2. Secondary Endpoints

- Biomarker: percent change in biomarker, CEMA, at the weeks 4, 8 and 12 visits during Phase 3 as compared to the last visit in Phase 2.
- Study cigarettes per day (CPD): the mean of study cigarettes smoked per day based on 7 days' Daily IVR-Revised data before the week 12 visit.
- Seven-day abstinence: if total CPD=0 for all 7 days before the week 12 visit and CO \leq 6ppm at week 12.

5.3. Exploratory Endpoint

- Non-combusted tobacco/nicotine products use: the number of days using any non-combusted tobacco/nicotine products in Phase 3.
- Characteristics' of products chosen (type, flavor, nicotine strength).
- Biomarkers: percent change in biomarkers (Total Nicotine Equivalents, total NNAL, mercapturic acids at the weeks 4, 8 and 12 visits during Phase 3 as compared to the last visit in Phase 2).
- Product satisfaction (Product Evaluation Scale if they used the product since the last visit; Cigarette Evaluation Scale if they smoked cigarettes since the last visit).
- Perceived health risk (Phase 1, Phase 2 and end of week 12 of Phase 3: all products for all subjects).
- Measures of discomfort/dysfunction: MNWS-R, QSU, CESD (NNC vs VLNC cigarettes irrespective of use of products).
- Dependence (FTND, WISDM, PATH items; monthly for study cigarettes).

